7.7.4 Urine Pharmacokinetic Concentrations

Collection of Urine Samples for PK Analysis (All SRD/MRD Cohorts)

| Sample Type | Dosing Day | Time post-dose (hours) | |
|-------------|------------|---|--|
| Urine | 1 | Predose (-12 to 0 hours) and at (0 to 6), (6 to 12), (12 to 24), (24 to 48), and (48 to 72) hour intervals postdose | |
| Urine | 18 | (0 to 6), (6 to 12), and (12 to 24) hour intervals postdose. | |

The amount of TAK-653, ^{CCI} in urine will be summarized by TAK-653 dose level and Day over each scheduled sampling interval using descriptive statistics (N, arithmetic mean, SD, median, minimum, and maximum). Individual urine concentration data versus time interval along with urine volume will be presented in a data listing.

7.7.5 Urine Pharmacokinetic Parameters

The PK parameters of urine TAK-653, ^{CCI} will be determined from urine concentrations for all evaluable subjects. The following PK parameters will be calculated using SAS version 9.3:

| Symbol/Term | Definition |
|-----------------|--|
| Ae _t | Amount of drug excreted in urine from time 0 to time t. |
| Ae _τ | Amount of drug excreted in urine during a dosing interval. |
| $f_{e,t} \\$ | Fraction of administered dose of drug excreted in urine from time 0 to time t. Molecular weight adjustment needed for metabolites (a). |
| CCI | |
| (a) CCI | |

Additional information regarding the urine PK analysis and urine PK parameter calculation and presentation will be provided in the CPAP. Additional urine PK parameters may be calculated if necessary, in accordance with the CPAP.

Descriptive statistics (N, arithmetic mean, SD, median, minimum, maximum and %CV) will be used to summarize the urine PK parameters for TAK-653, ^{CCI} by TAK-653 dose level and Day. Individual urine PK parameters will be presented in a data listing.

Pharmacodynamic Analysis 7.7.6

Collection of Blood Samples for PD Analysis of ^{CCI}

| Sample Type | Study Day | Time Points |
|--------------------|--------------------|--|
| SRD (Cohort 6 onwa | rd) and SRD/MRD (C | ohort 3 onward) |
| Serum | 1 | Predose and at 4, 8, and 12 hours postdose |
| Serum | 2-5 | 24, 48, 72, and 96 hours postdose |
| SRD/MRD (Cohort 3 | onward) | |
| Serum | 18 | Predose and at 4, 8, and 12 hours postdose |
| Serum | 19 | 24 hours postdose |

Note: Hemolyzed PD samples will not be redrawn.

Note: A single dose is administered on Day 1. No additional doses are administered until Day 6 when QD dosing begins from Day 6 through 18.

PD Parameters for ^{CCI}

| Symbol/Term | Definition |
|------------------|---|
| AUEC | Area under the effect-time curve over 96 hours after a single dose and over 24 hours after multiple dosing. |
| E _{max} | Maximum observed effect. |

| CCI | | |
|-----|--|--|
| | | |
| | | |
| | | |
| | | |
| | | |
| | | |
| | | |
| | | |
| | | |
| | | |
| | | |
| | | |
| | | |
| | | |
| | | |
| | | |
| | | |

7.7.7 CCI Pharmacodynamic Parameters

All the analyses, including data listings, for this section will be performed independently outside this document.

7.8 Other Outcomes

Not applicable.

7.9 Safety Analysis

For each part, data for all subjects in the safety analyses set will be summarized by pooled placebo and each TAK-653 dose level for clinical laboratory, vital signs, ECG, and C-SSRS results, and by pooled placebo, each TAK-653 dose level, pooled TAK-653, and overall total for other safety variables. These summaries will not contain data from the food effect cohort (SRD Cohort 3); data from this cohort will be summarized separately by placebo fed, placebo fasted, TAK-653 fed, and TAK-653 fasted.

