#### 13.1.4 Pharmacodynamic Analysis

## 13.1.5 Safety Analysis

All safety data will be presented in listings. Where applicable, within each part, safety data will be summarized by placebo, each TAK-653 dose level, TAK-653 overall, and overall total. Placebo data will be pooled across cohorts within each part. These summaries will not contain data from the fed portion. Data from the food effect cohort will be summarized separately by placebo fed, placebo fasted, TAK-653 fed, and TAK-653 fasted.

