|---------------------|--------------------------------|--|--|--|--|------------------|
| Screening | Check-in Assessments (a) | TAK-653 Dosing Study Assessments (a) (b) (c) | Safety and PK Assessments (a) (c) | PK Assessments | PK Assessments/ Study Exit (a) | |
| Day -28 to -2 | Day -1 | Day 1 | Days 2-5 | Day 6 (Cohorts 1-5) Days 6-7 (Cohort 6 onward) | Day 7 (Cohorts 1-5) Day 8 (Cohort 6 onward) | Day 14 (±2) |
| | ← | Confinement — | > | | | |

Part 1: SRD Study Schematic

(a) EEG assessments are scheduled on Days -1, 1, 2, and 5, at Study Exit, and at ET.

(b) Study assessments include PK sample collection throughout.

(c) CC

(d) Follow-up will occur by telephone unless abnormal, clinically significant findings are observed upon discharge. In this case or at investigator's discretion, subjects should return to the clinic for re-evaluation.

The planned first dose level to be studied is 0.3 mg for SRD Cohort 1. The actual choice of the dose levels in subsequent Cohorts will occur after the full review of all available blinded safety, tolerability, PK, and PD data in the preceding cohorts. If necessary, the sponsor team (Takeda only) may unblind the data and perform additional analyses for an informed dose-escalation

| TAK-653-1001 | Page 9 of 32 |
|---------------------------------|----------------|
| Statistical Analysis Plan Final | 22 August 2017 |

decision. The next dose level may be higher, lower, or remain the same as the preceding dose level. If the dose is not increased in the next Cohort, staggered dosing is not necessary.

| | TAK-653 Single Dose (b) (c) | | |
|-------------------------------|-----------------------------|---------|-------------------------|
| Cohort (a) | Planned | Actual | No. of Subjects |
| 1 | 0.3 mg | 0.3 mg | 6 TAK-653 2 placebo |
| 2 | X mg | 1.0 mg | 6 TAK-653 2 placebo |
| 3 (food-effect cohort) (d) | X mg | 3.0 mg | 6 TAK-653 2 placebo |
| 4 | X mg | 5.0 mg | 6 TAK-653 2 placebo |
| 5 | X mg | 9.0 mg | 6 TAK-653 2 placebo |
| 6 | X mg | 18.0 mg | 6 TAK-6536 2 placebo |

Part 1: Summary of SRD Dose Cohorts

(a) Sentinel dosing will occur at the start of each Cohort in the SRD. After the investigator and sponsor review the 24-hour safety and tolerability data, the remaining subjects can be dosed in a staggered fashion (no more than 3 subjects at a time). A 24-hour gap will follow each subsequent administration to evaluate safety and tolerability data.

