7.0 METHODS OF ANALYSIS AND PRESENTATION

7.1 General Principles

All study-related raw and derived data will be presented in data listings as appropriate. Continuous data will be summarized using number of subjects (N), mean, standard deviation (SD), median, minimum, and maximum, where appropriate. Where indicated, coefficient of variation (%CV) and geometric mean will also be included in the summary of continuous data. Categorical data will be summarized using the number and percentage of subjects for each category where appropriate.

All statistical tests will be 2-tailed at α =0.05 level for significance unless otherwise stated. The p-values less than or equal to α (when rounded to 3 digits) are reported as "significant". The phrase "no significant difference" indicates that all p-values for the tests are greater than α . All computations will be performed prior to rounding.

Subjects who take placebo in each cohort group will be pooled together in all safety summaries for each part (Part 1 and Part 2) and will be analyzed as one placebo group.

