7.1.3 Definition of Study Days and Baseline

For all safety endpoints, Baseline is defined as the last non-missing measurement prior to first dose of study drug for Part 1 SRD Cohorts and Part 2 SRD/MRD Cohorts. Baseline is defined as the last non-missing measurement prior to the first dose of study drug in each period (fed and fasted) for Part 1 Food Effect Cohort. Study day will be calculated relative to the date of the first dose in the study. Study day prior to the first dose of treatment will be calculated as: date of assessment/event – date of treatment; study day on or after the date of first dose of treatment will be calculated as: date of assessment/event – date of treatment + 1.

| TAK-653-1001 | Page 17 of 32 |
|---------------------------------|----------------|
| Statistical Analysis Plan Final | 22 August 2017 |

| 7.2 | Analysis Sets | |
|--------|------------------|---|
| Safety | ⁷ Set | The safety set will consist of all subjects who are enrolled and received 1 dose of study drug. Subjects in this analysis set will be used for demographic, other baseline characteristic, and safety summaries. |
| Rando | omized Set | The randomized set will consist of all subjects who are enrolled and randomized. |
| PK Se | et | The PK set will consist of all subjects who receive study drug and have at least 1 measurable plasma concentration or amount of drug in the urine. |
| PD Se | t | The PD set will consist of all subjects who receive study drug and have at least 1 postdose PD measurement. |

If any subjects are found to be noncompliant in dosing schedule or to have incomplete data, a decision will be made on a case-by-case basis as to their inclusion in the analysis but data for these subjects will be presented in the data listings.

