Additionally, box plots of TAK-653 dose-normalized C_{max} and AUCs versus dose will be provided for each part (fasted cohorts only). Box plots of TAK-653 C_{max} and AUCs comparing fasted versus fed cohorts will also be provided.

Dose proportionality will be tested for SRD cohorts (fasted cohorts only) on Day 1 and for SRD/MRD cohorts after multiple dosing on Day 18 for TAK-653 C_{max} and AUCs using a power model. The power fit will be assumed as described by the following equation:

 $\ln(PK \ Parameter) = \beta_0 + \beta_1 \ln(Dose) + \varepsilon$

where β_0 is the intercept and β_1 is the slope. The dose proportionality will be declared when the 90% confidence interval for β_1 lies entirely within the critical region.

$$\left(1 + \frac{\ln(0.80)}{\ln(r)}, 1 + \frac{\ln(1.25)}{\ln(r)}\right)$$

where r is the ratio of the highest and the lowest dose in this study. This criterion implies that the 90% CI for the ratio of the central values of PK parameter of interest from the highest dose to the lowest dose is contained completely within the bioequivalence range of (0.80, 1.25) [2]. Plots of ln(AUC) or ln(C_{max}) vs ln(Dose) may also be used to illustrate dose proportionality or lack of it.

A power model will be performed to test whether the slope=1 in the power model and whether the point estimate of the slope is significantly different from 0 or not.

The effect of food on the PK of TAK-653 will be evaluated via a paired t-test. The point estimates and 90% CIs for the ratio of C_{max} and AUC central values for TAK-653 tablets administered after fed conditions vs those obtained in the fasted state will be determined. The food effect on t_{max} will also be evaluated using a non-parametric Wilcoxon rank sum test.

All attempts will be made to have a distribution of ^{CCI} times within the prescribed window of 2 to 6 hours postdose on Day 12 for SRD/MRD Cohort 3; for example, the ^{CCI} may be collected at 2 hours postdose from the first subject, 3 hours postdose from the

| TAK-653-1001 | Page 22 of 32 |
|---------------------------------|----------------|
| Statistical Analysis Plan Final | 22 August 2017 |
| | |

second subject, 4 hours postdose from the third subject, and 6 hours postdose from the fourth subject with a collection window of +1 hour for each subject.

| The CCI | , if available, will be presented |
|--|---------------------------------------|
| in a data listing. The ratio of TAK-653 ^{COI} | on Day 12 to the TAK-653 plasma |

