7.11 Changes in the Statistical Analysis Plan

The analysis for EEG pharmacodynamic parameters outlined in the Section of 13.1.4 in Protocol TAK-653-1001 [1] will be performed outside this SAP.

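### SAP 7.9 drops all of SRD Cohort 3, including its fasted 3 mg dose, from the main Part 1 safety tables; the protocol drops only the fed data, and the change is undeclared

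*SAP*

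**What the plan says.** Protocol 13.1.5 summarizes safety within each part by placebo, each dose level, TAK-653 overall and total. Its rule is "Placebo data will be pooled across cohorts within each part. These summaries will not contain data from the fed portion". It then adds a separate summary of the food-effect cohort in four columns, by treatment and by fed or fasted state.

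SAP 7.9 plans the same kind of table. Laboratory, vital signs, ECG and C-SSRS results are shown by pooled placebo and each dose level. The remaining safety variables, adverse events among them, are shown "by pooled placebo, each TAK-653 dose level, pooled TAK-653, and overall total for other safety variables". The exclusion, however, is worded differently: "These summaries will not contain data from the food effect cohort (SRD Cohort 3); data from this cohort will be summarized separately", in the same four columns as in the protocol.

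Three other parts of the SAP bear on this:

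- Section 7.1 states a general rule with no exception for Cohort 3: "Subjects who take placebo in each cohort group will be pooled together in all safety summaries for each part".
- Section 7.7.2 restricts the PK analysis by fed state, not by cohort: "Dose proportionality will be tested for SRD cohorts (fasted cohorts only) on Day 1".
- Section 7.11, which records changes, lists one item only: "The analysis for EEG pharmacodynamic parameters outlined in the Section of 13.1.4", to be done outside the SAP.

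The Part 1 cohort table in SAP 4.4 identifies Cohort 3 as the food-effect cohort, at 3.0 mg with 6 active and 2 placebo subjects. It is the only 3 mg cohort in Part 1. Its subjects were dosed fasted, like every other SRD cohort, before returning for the fed dose.

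**The concern.** The two documents exclude different things. The protocol excludes a period (fed); the SAP excludes a cohort. The difference between them is the fasted period of Cohort 3, which is part of the dose-escalation sequence.

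Most of the primary endpoints are percentages of subjects (SAP 5.1), so who is in a table matters. A Part 1 safety table that runs 0.3, 1, 5, 9 and 18 mg has a gap in the middle of the dose series. It also has a placebo group without the Cohort 3 placebo subjects. The SAP cites Amendment 6 of the protocol as its source, yet a reader comparing the two would find no notice of the change. Disposition (SAP 7.3) and demographics (SAP 7.4) are tabulated by the same columns without the exclusion, so their Part 1 denominators would not match those of the safety tables.

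**Working it through.** **Step 1: can the two rules be read as the same?** The protocol has two consecutive sentences. One removes the fed portion from the main summaries; the next adds a separate fed/fasted summary of the cohort. If the second were meant to take the whole cohort out of the main tables, the first would have no purpose. Under the protocol, then, fasted Cohort 3 data appear twice: in the main tables and in the separate one. Under SAP 7.9 they appear only in the separate one.

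**Step 2: is the SAP consistent with itself?** No, in two places. Section 7.1 pools the placebo subjects of each cohort in every safety summary of a part, whereas 7.9 leaves out those of Cohort 3. And 7.9 itself begins by covering all subjects in the safety set at each dose level, then removes one cohort and, with it, the only Part 1 cohort at one dose level.

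**Step 3: inputs for the counts.**

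- Allocation per cohort: 6 active, 2 placebo (Protocol 6.1; SAP 4.4).
- SRD cohorts: six in the SAP 4.4 table (0.3, 1, 3, 5, 9, 18 mg).
- Assumption: all cohorts full, no replacements.
- Check on the allocation: Protocol 4.3 reports 56 subjects, 42 active and 14 placebo, in seven completed cohorts. 7 × 8 = 56, 7 × 6 = 42 and 7 × 2 = 14, which agree.

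The documents give no denominators for the safety tables, so there is no plan figure to reproduce.

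**Step 4: Part 1 denominators.**

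| Column | Protocol rule | SAP 7.9 as written | Change |
|---|---|---|---|
| 3 mg (fasted) | 6 | column absent | – |
| Pooled placebo | 6 × 2 = 12 | 12 − 2 = 10 | 2/12 = 16.7% |
| Pooled TAK-653* | 6 × 6 = 36 | 36 − 6 = 30 | 6/36 = 16.7% |
| Overall* | 48 | 48 − 8 = 40 | 8/48 = 16.7% |

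*Planned for adverse events and other variables, not for laboratory, vital signs, ECG or C-SSRS.

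With only the five cohorts of Protocol Table 6.a, the overall total would go from 40 to 32 (30 + 10 to 24 + 8).

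**Step 5: an illustration of precision.** The SAP plans no confidence limits for safety percentages, so this serves only as a scale. With zero events in n subjects, the one-sided 95% upper limit for the event rate is 1 − 0.05^(1/n).

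- Pooled placebo: n = 12 gives 22.1%; n = 10 gives 25.9%.
- Pooled TAK-653: n = 36 gives 8.0%; n = 30 gives 9.5%.

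**The case against.** The strongest case on the other side is that this is loose wording with little consequence. The 7.9 sentence looks like the two protocol sentences merged into one, and the documents elsewhere use the word cohort for the fed period (Protocol 13.1.3.2 speaks of a fed cohort; SAP 7.7.2 compares fasted and fed cohorts). The authors may have meant only the fed data. The opening of 7.9 also points that way, so the missing 3 mg column is not beyond doubt. This stands as a caution about intent, but it does not rescue the text: the sentence names SRD Cohort 3 and sends its fasted results to the separate table. A programmer who follows it would filter by cohort.

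Three stronger readings are tempting, and the documents do not support them.

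- *A reader might infer that the 3 mg safety data are lost.* They are not. They stay in the listings, and the fasted 3 mg group has its own column in the separate table. Cohort 3 also remains in the Safety Set.
- *A reader might infer that the placebo comparator for 3 mg shrinks from 12 to 2.* The fed/fasted table with its 2 fasted placebo subjects is required by the protocol too, so that table does not change. The main Part 1 table would still show 10 pooled placebo subjects. The real change is 12 to 10.
- *A reader might infer that every primary endpoint is affected.* Discontinuation reasons are tabulated in SAP 7.3 by the same columns without excluding Cohort 3, and a pretreatment or adverse event is one of the reason categories in Protocol 7.5. The effect is confined to the tables under 7.9.

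**Conclusion.** The concern holds as a mismatch between protocol and SAP that is undeclared in 7.11 and contradicts SAP 7.1 and the opening of 7.9. Read literally, the 7.9 tables for Part 1 lack the 3 mg column, and each pooled column that is planned loses one sixth of its subjects. These sizes assume six full SRD cohorts at 6:2.

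The consequence is moderate. The safety analyses are descriptive, the sample size was not based on power, and Part 2, which has its own 3 mg cohort, is untouched. The matter is one of completeness and traceability in the main Part 1 safety tables. It should be fixed, because the correction is small and the tables carry most of the primary endpoints.

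**What to change.** 1. Replace the exclusion sentence in SAP 7.9 with the protocol rule: the main Part 1 safety summaries exclude fed-period data only. Fasted-period data from SRD Cohort 3, active and placebo, stay in the 3 mg and pooled-placebo columns and, where present, in the pooled TAK-653 and overall columns.
2. Keep the separate fed/fasted table as an addition, and name it in SAP 7.1 as the one exception to placebo pooling.
3. State how events and measurements are assigned to a period, and use the same rule in both sets of tables; for example, the fasted period runs from the fasted dose up to the fed dose. This is needed because the adverse-event window (30 days) and the window for markedly abnormal values (7 days) are both counted from the last dose, and this cohort is dosed twice.
4. If excluding the whole cohort is intended, declare and justify it in 7.11, and align 7.1 and the opening of 7.9.

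The cost is one sentence in 7.9, one clause in 7.1, a short period-assignment rule, and a programming filter on period instead of cohort. The separate table already requires each record to be assigned to a period, and SAP 7.1.3 already sets the baseline for this cohort by period: "Baseline is defined as the last non-missing measurement prior to the first dose of study drug in each period (fed and fasted"). No additional data are needed.

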7.9.1 Adverse Events

A TEAE will be defined as an AE or a SAE that occurs or gets worse after receiving the first dose of study drug and within 30 days (onset date – last date of dose + $1 \le 30$) after the last dose of study drug. A TEAE may also be a pretreatment event (PTE) or a concurrent medical condition diagnosed prior to the date of first dose of study drug that increases in severity after the start of dosing. Adverse events data with onset occurring more than 30 days after last dose of study drug (AE start date – last dose date >30) will be listed, but not included in the summary tables.

AE verbatim reported terms will be coded by system organ class (SOC), high-level term (HLT) and preferred term (PT) using MedDRA.

The following is a list of AE summary tables that will be generated:

- Overview of TEAE.
- TEAEs by SOC and PT at subject and event level.
- Subject Mappings for TEAEs.
- TEAEs by PT.
- Non-Serious TEAEs by PT.

- Relationship of TEAEs to Study Drug by SOC and PT.
- Drug-Related TEAEs by SOC and PT.
- Intensity of TEAEs by SOC and PT.
- Intensity of Drug-Related TEAEs by SOC and PT.
- PTEs by SOC and PT
- Serious PTEs by SOC and PT.

A subject with 2 or more different AEs within the same level of the MedDRA term will be counted only once in that level using the most extreme incident for the intensity tables, and relationship to study drug for the causality tables.

Data listings will be provided for all AEs (including PTEs for enrolled subjects), AEs leading to study drug discontinuation, AEs leading to study visit discontinuation, SAEs, and AEs resulting in death.

7.9.2 Clinical Laboratory Evaluations

Clinical laboratory tests include hematology, serum chemistry and urinalysis.

Descriptive statistics (N, mean, median, SD, minimum and maximum) of clinical laboratory variables in SI units will be summarized for Baseline, postdose, and change from Baseline at each visit. Only the scheduled measurements will be included in the summary. No statistical tests will be performed.

Individual results for hematology and chemistry laboratory tests will be evaluated against the Takeda predefined laboratory markedly abnormal value (MAV) criteria (Appendix A) using the result and criteria in SI units. All subjects with results that meet the MAV criteria will be presented in a data listing. The number and percentage of subjects with at least one postdose markedly abnormal laboratory test result will also be summarized. The mapping of the subjects who meet the MAV criteria after dosing will be listed as a table. All postdose clinical laboratory results within 7 days of the last dose, including scheduled and unscheduled measurements, will be included in the MAV summaries.

All clinical laboratory data will be presented in both SI and conventional units in data listings.

7.9.3 Vital Signs

Vital signs will include body temperature (oral), supine blood pressure (resting more than 5 minutes), respiration rate, and heart rate. Heart rate and blood pressure will be measured after 5 minutes supine and again at 1 and 3 minutes after standing.

Descriptive statistics (N, mean, median, SD, minimum and maximum) of these vital signs will be summarized for Baseline, postdose, and change from Baseline at each visit. Only the vital signs collected at the scheduled visits or time points will be included in the summary. No statistical tests will be performed for the observed vital signs.

| TAK-653-1001 | Page 26 of 32 |
|---------------------------------|----------------|
| Statistical Analysis Plan Final | 22 August 2017 |

All individual vital signs that meet Takeda's predefined MAV criteria (Appendix B) will be listed. The number and percentage of subjects with at least one postdose markedly abnormal vital sign measurement will be summarized. The mapping of the subjects who meet the MAV criteria after dosing will be listed as a table. All postdose vital signs within 7 days of the last dose, including both scheduled and unscheduled measurements, will be included in the MAV summaries.

7.9.4 12-Lead ECGs

ECG measurements include clinical interpretation, heart rate, and PR, QRS, RR, QT, and QTcF intervals.

Descriptive statistics (N, mean, SD, median, minimum, and maximum) of the quantitative ECG will be summarized for Baseline, postdose, and change from Baseline at each visit. Only the ECGs collected at the scheduled visits or time points will be included in the summary. No statistical tests will be performed for the observed ECGs.

All individual ECGs that meet Takeda's predefined MAV criteria (Appendix C) will be listed. The number and percentage of subjects with at least one postdose markedly abnormal ECG measurement will be summarized. Subjects who meet the MAV criteria after dosing will be mapped to their respective qualifying ECG result. All postdose MAV ECGs within 7 days of the last dose, including both scheduled and unscheduled measurements, will be included in the MAV summaries.

For ECG interpretation data, shift tables will be provided for the number and percentage of subjects who change status on the interpretation from Baseline to each scheduled postbaseline measurement.

All ECG data will be presented in data listings.

